2.2 Secondary

- 2.2.1 To assess the safety of PEA at the two study doses.
- 2.2.2 To evaluate changes in patient-reported quality of life from baseline to the end of 8 weeks.

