16.2 Sample size, Accrual time and Study Duration

16.2.1 Sample size

As this is a pilot trial to estimate the efficacy of PEA, the sample size is based on feasibility considerations and estimation precision. We plan to accrue a total of 88 patients (consisting of 78 evaluable patients + 10% dropout due to cancellation or ineligibility). Based on our previous trial experience [98], by assuming the standard deviation of the 0-100 scale transformed CIPN20 change score is 15 in each treatment arm. With this assumption, 26 patients per PEA arm and 26 total patients for the combined placebo arm (pooling all patients receiving

placebo together for statistical analysis) allows estimation of the difference between two arms, of the CIPN20 score change from baseline to 8 weeks, with a 95% two-sided confidence interval width of 16.8 points.

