16.4.1 Secondary endpoint analysis

16.4.1.1 Adverse events by patient will be summarized by frequencies and severity using CTCAE v5.0. The proportion of patients who experience at least one grade 3+ adverse event (regardless of attribution) will be reported. The overall adverse event rates for grade 3 or higher adverse events will be compared across the three arms (the two PEA arms and combined placebo) using a Chi-squared or Fisher's Exact tests as appropriate.

16.4.1.2 The difference in change of QOL (Question 3 [Appendix V](#), PRO-QOL) from baseline to 8 weeks will be calculated for each patient. The mean and standard deviation of the change will be reported for each PEA arm

and the combined placebo arm. Additional analysis using data collected from the Symptom Experience Diary may be performed. For patients who go off protocol treatment before 8 weeks, the question 3 response at their final observation will be used to calculate the change. For patients who do not have any post baseline data, they will be considered to have no change from baseline.

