16.4.2 Exploratory endpoint analysis

16.4.2.1 The two cognitive items of the Cognitive Functioning Assessment ([Appendix VII](#)) will be summarized by mean (SD) and median (range) at each time point for each PEA arm and the combined placebo arm. The mean change from baseline to 8 weeks will be estimated along with the 95% confidence interval for each PEA arm and the combined placebo arm.

16.4.2.2 The weekly CIPN20 scores will be summarized at each time point by mean (SD) and median (range) and will be plotted longitudinally for each PEA arm and the combined placebo arm.

16.4.2.3 The weekly pain scores ([Appendix VI](#)) will be summarized at each time point by mean (SD) and median (range) and will be plotted longitudinally for each PEA arm and the combined placebo arm.

16.4.2.4 Items of the Global Impression of Change tool ([Appendix III](#)) will be summarized by frequency (percentage) of each level at each time point for each PEA arm and the combined placebo arm. Bar plots for each PEA arm and the combined placebo arm of frequency over time will be constructed.

16.4.2.5 The Chemotherapy Induced Peripheral Neuropathy Assessment Tool ([Appendix IV](#)) will be summarized by mean (SD) and median (range) at each time point for each PEA arm and the combined placebo arm.

16.4.2.6 Using the changes scores constructed for the primary endpoint, the difference in CIPN20 change scores between the two PEA dosage arms will be estimated along with a 95% confidence interval.

16.4.2.7 Evidence of disease recurrence and the date of recurrence will be asked by nurse at the 6 and 12 months' follow-up ([Appendix IX](#)). The number of events and percentage will be reported by each PEA arm and combined placebo arm. No hypothesis test will be performed between arms.

16.4.2.8 Overall survival is defined as the time from registration to death due to any cause. For each PEA arm and combined placebo arm, the distributions of OS time will be estimated using the Kaplan-Meier method. Log-rank test will be used to compare the survival distributions between each PEA and the combined placebo arm.

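### The only named between-arm tests are on grade 3+ adverse events and overall survival, both weak at about 26 per arm, and no confidence interval is planned for either outcome

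*Combined protocol and SAP*

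**What the plan says.** Section 16.2.1 states that "the sample size is based on feasibility considerations and estimation precision". The primary contrast (16.3.1) and the dose-versus-dose contrast (16.4.2.6) are differences in CIPN20 change with 95% confidence intervals, and no test is named for either. The cognitive items (16.4.2.1) get within-arm intervals.

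Two outcomes are handled differently:

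- **Grade 3+ adverse events.** Section 16.4.1.1 reports the proportion of patients with at least one event, regardless of attribution. It then says that the "rates for grade 3 or higher adverse events will be compared across the three arms", by Chi-squared or Fisher's exact test as suits the data.
- **Overall survival.** Section 16.4.2.8 plans Kaplan-Meier curves and adds: "Log-rank test will be used to compare the survival distributions between each PEA and the combined placebo arm".

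No interval is specified for an adverse event proportion, a difference in proportions, a Kaplan-Meier estimate or a hazard ratio. No significance level, expected rate or power is given for either test. For recurrence, the neighbouring Section 16.4.2.7 says: "No hypothesis test will be performed between arms". The safety objective (2.2.1) reads: "To assess the safety of PEA at the two study doses".

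**The concern.** The objective concerns two doses, but the planned comparison is a single global test over three groups. Such a test does not say which dose differs or by how much, and it treats an excess on placebo like an excess on PEA. In a pilot of this size it will usually be non-significant, and that result does not show what rate of harm remains compatible with the data. An interval would show this, and the plan does not ask for one.

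For survival, follow-up ends at 12 months (Section 4.1) and evidence of residual cancer is an exclusion (Section 3.2.3). If deaths are few, the large-sample log-rank p-value has little behind it. The plan gives no reason for testing death while ruling out a test for recurrence.

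At stake is how informative the safety results will be to the team designing the phase III trial.

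**Working it through.** **Inputs from the documents.** Section 16.2.1 plans "26 patients per PEA arm and 26 total patients for the combined placebo arm" and assumes that "the standard deviation of the 0-100 scale transformed CIPN20 change score is 15 in each treatment arm". The allowance from 78 to 88 patients covers cancellation and ineligibility. A cancelled patient is never treated (13.5), and the safety set is eligible patients with at least one dose (16.4). The planned safety set is therefore about 78/3 = 26 per analysed group, not 88/3 = 29.

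**Assumptions.** Two-sided alpha 0.05; grade 3+ rates of 1% to 30%; one-year survival of 90% to 98%. The documents give none of these.

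**The plan's own figure.** Width = 2 × t(0.975, 50 df) × 15 × √(2/26) = 2 × 2.009 × 15 × 0.2774 = 16.71 (16.31 with 1.96). Rounding the half-width of 8.36 to 8.4 and doubling gives the stated result, "with a 95% two-sided confidence interval width of 16.8 points". The estimation design reproduces. Neither test has a corresponding design figure.

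**Adverse event test.** Full enumeration of three Binomial(26, p) arms with the Fisher-Freeman-Halton test:

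| Rates, placebo/400/800 | Probability of p ≤ 0.05 |
|---|---|
| 1/1/1% (size) | 0.02% |
| 2/2/2% (size) | 0.2% |
| 5/5/5% (size) | 1.4% |
| 10/10/10% (size) | 3.1% |
| 5/15/15% | 15% |
| 5/5/20% | 36% |
| 5/5/30% | 72% |

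Chi-squared is little different: 15% at 5/15/15% and 39% at 5/5/20%.

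Particular tables show the same weakness. With no events in the other two arms, 3 events in one arm give Fisher p = 0.10 and 4 give p = 0.031. Three events in each PEA arm and none on placebo, which is 6 v 0 for active against placebo, give p = 0.24.

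**What intervals would give.**

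- Exact upper 95% limit for 0/n is 1 − 0.025^(1/n): 13.2% for n = 26, and 6.8% for n = 52 (both doses).
- Exact 95% interval for 2/26: 0.9% to 25.1%.
- Newcombe 95% interval for the difference between two arms of 26: 0 v 0 events, −12.9 to +12.9 points; 2 v 1, −12.2 to +20.6; 4 v 1, −6.1 to +30.0.

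**Log-rank test, 26 v 26.** Expected deaths in the pair under no effect are 52 × (1 − S): 1.0, 2.6 and 5.2 for S = 98%, 95% and 90%. Simulation with 4,000 runs per setting gives:

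| One-year survival, placebo | Size | Power, HR 2 |
|---|---|---|
| 98% | 0.2% | 1% |
| 95% | 2.1% | 8% |
| 90% | 5.1% | 15% |

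Schoenfeld's formula for 80% power at HR 2 gives 4 × (1.960 + 0.842)²/(ln 2)², or 66 deaths after rounding up. A pair has only 52 patients.

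Suppose 4 deaths all fall in one arm. E = 26/52 + 25/51 + 24/50 + 23/49 = 1.940 and V = 0.999, so chi-squared = (4 − 1.940)²/0.999 = 4.25 and p = 0.039. The exact permutation p-value is 2 × C(26,4)/C(52,4) = 2 × 14,950/270,725 = 0.110. For a 5-0 split the two p-values are 0.020 and 0.051. For 6-0 they are 0.010 and 0.023.

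**The case against.** The strongest reply is that both tests are legitimate. Fisher's exact test is provided for, and it is conservative. The size of the log-rank test is not materially inflated in simulation, and a split such as 4-0 is unusual under no effect. That reply stands. A reader might infer from the sparse data that the tests are invalid, and the calculations do not support this. What remains is that the asymptotic p-value is unreliable in the sparse tables where it would attract attention.

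A reader might also infer that the plan tests its rarest outcomes, or that recurrence will outnumber death. The documents give no rates for any of these. Adverse events count regardless of attribution, and ECOG 2 and a history of metastatic cancer are allowed (3.1.2), so neither adverse events nor deaths need be very rare.

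It is also fair to say that low power for safety tests is normal in a pilot, that survival is exploratory, and that no decision rule uses either p-value. Adverse events are also summarised by frequency and severity, there is a stopping rule (16.6.1), and the data safety monitoring board receives reports every six months (16.7). The documents therefore do not support a claim that safety goes unexamined or that a p-value will drive the phase III decision. None of this supplies the missing per-dose estimate. Readers could derive exact intervals for proportions from the reported counts, but the plan should specify its main safety comparison.

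**Conclusion.** The point holds as a mismatch between an estimation design and its safety analysis. The two named tests are the only between-arm tests in the plan. Neither outcome has a planned interval, and the global adverse event test does not answer objective 2.2.1. At 26 per arm its power is 36% for 5/5/20% and 15% for 5/15/15%. Log-rank power for a hazard ratio of 2 is at most about 15% over the survival range examined. These figures rest on an assumed 5% level and assumed event rates. More frequent events would change them: at 5/5/30%, Fisher power reaches 72%. The need for a per-dose estimate with an interval does not depend on those assumptions.

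The consequence is limited to one secondary and one exploratory analysis. The improvement is worth making because it costs almost nothing.

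**What to change.** **Section 16.4.1.1.** Report the grade 3+ proportion with an exact (Clopper-Pearson) 95% interval for each PEA arm and combined placebo. Make the risk difference with 95% interval (for example Newcombe) for each dose against combined placebo the main safety comparison. Both doses pooled against placebo can be added as an option. Keep the three-arm test, if at all, as descriptive.

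**Section 16.4.2.8.** Report deaths by arm and the 12-month Kaplan-Meier estimate with 95% interval. Either drop the log-rank test, in line with 16.4.2.7 for recurrence, or label it descriptive and use an exact or permutation version. Deleting it is not essential. If it stays, add a sentence on why survival is tested and recurrence is not.

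**Cost.** SAP wording and a few table cells. No new data, no change in sample size, and no effect on the primary analysis.

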16.4.2 Exploratory endpoint analysis

16.4.2.1 The two cognitive items of the Cognitive Functioning Assessment ([Appendix VII](#)) will be summarized by mean (SD) and median (range) at each time point for each PEA arm and the combined placebo arm. The mean change from baseline to 8 weeks will be estimated along with the 95% confidence interval for each PEA arm and the combined placebo arm.

16.4.2.2 The weekly CIPN20 scores will be summarized at each time point by mean (SD) and median (range) and will be plotted longitudinally for each PEA arm and the combined placebo arm.

16.4.2.3 The weekly pain scores ([Appendix VI](#)) will be summarized at each time point by mean (SD) and median (range) and will be plotted longitudinally for each PEA arm and the combined placebo arm.

16.4.2.4 Items of the Global Impression of Change tool ([Appendix III](#)) will be summarized by frequency (percentage) of each level at each time point for each PEA arm and the combined placebo arm. Bar plots for each PEA arm and the combined placebo arm of frequency over time will be constructed.

16.4.2.5 The Chemotherapy Induced Peripheral Neuropathy Assessment Tool ([Appendix IV](#)) will be summarized by mean (SD) and median (range) at each time point for each PEA arm and the combined placebo arm.

16.4.2.6 Using the changes scores constructed for the primary endpoint, the difference in CIPN20 change scores between the two PEA dosage arms will be estimated along with a 95% confidence interval.

16.4.2.7 Evidence of disease recurrence and the date of recurrence will be asked by nurse at the 6 and 12 months' follow-up ([Appendix IX](#)). The number of events and percentage will be reported by each PEA arm and combined placebo arm. No hypothesis test will be performed between arms.

16.4.2.8 Overall survival is defined as the time from registration to death due to any cause. For each PEA arm and combined placebo arm, the distributions of OS time will be estimated using the Kaplan-Meier method. Log-rank test will be used to compare the survival distributions between each PEA and the combined placebo arm.

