2.3 Exploratory

- 2.3.1 To explore whether PEA appears to affect cognition in the study patients.
- 2.3.2 To explore the weekly trajectory of CIPN from baseline to 8 weeks.
- 2.3.3 To explore the weekly trajectory of pain using the single-item numerical rating scale from baseline to 8 weeks.
- 2.3.4 To explore the weekly patient global impression of change in each treatment arm from baseline to 8 weeks.
- 2.3.5 To explore the weekly chemotherapy induced peripheral neuropathy in each treatment arm from baseline to 8 weeks.
- 2.3.6 To explore the PEA effects on CIPN20 between two PEA dosage arms.
- 2.3.7 To explore the number of recurrent cancer events by study arm
- 2.3.8 To explore the overall survival by study arm

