16.0 Statistical Considerations

16.1 Statistical Design

This trial is designed as a randomized placebo-controlled pilot trial with the primary objective of estimating the efficacy of two dose levels of PEA to inform the design of a future phase III trial for treatment of chemotherapy-induced peripheral neuropathy (CIPN). Patients will be randomized 2:2:1:1 to receive either 400 mg of PEA (one 400 mg capsule), 800 mg PEA (two 400 mg capsules), 1 placebo capsule, or 2 placebo capsules, respectively. The two placebo arms are included in this study to ensure that there is a matched number of capsules for each of the PEA arms; however, all placebo patients will be analyzed as one group (a combined placebo arm). The efficacy of the two dose levels of PEA will be estimated as the difference between each dose level of PEA compared to the combined placebo arm.

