16.3 Primary Endpoint Analysis Plan

16.3.1 Primary endpoint analysis

The primary endpoint is the CIPN20 score ([Appendix II](#)). The CIPN20 questionnaire will be scored and summarized at each time point for each patient (see Section 11.1). The change from baseline to 8 weeks will then be calculated for each patient. The mean (standard deviation) and median (range) of the change will be calculated for each PEA arm and the combined placebo arm. The difference in change scores between each PEA arm and the combined placebo will be estimated along with a 95% confidence interval. For the primary analysis, the CIPN20 analysis dataset will include all eligible patients who are randomized, initiated treatment, and completed the baseline questionnaire. For patients who go off protocol treatment before 8 weeks, the score at their final observation will be used to calculate the change. For patients who do not have any post baseline data, they will be considered to have no change from baseline. Sensitivity analysis based on imputation of missing data as described in Section 16.5 will be performed using similar methods.

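### The weekly CIPN20 scores are routinely summarised and plotted by arm only, so the trajectory objective (2.3.2) has no PEA-minus-placebo estimate or interval over time

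*Combined protocol and SAP*

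**What the plan says.** All references are to the combined protocol and SAP.

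- **Data collected.** Sections 4.0 and 11.1.1 schedule the CIPN20 at baseline and at the end of each of eight treatment weeks.
- **Primary estimate (16.3.1).** "The change from baseline to 8 weeks will then be calculated for each patient". Each PEA arm is compared with combined placebo by a difference and 95% interval. A patient who stops treatment early contributes the last score, and a patient with no post-baseline score is given zero change.
- **Dose comparison (16.4.2.6).** The same change scores are used for a difference and 95% interval between the two PEA arms.
- **Trajectory objective (2.3.2).** "To explore the weekly trajectory of CIPN from baseline to 8 weeks".
- **Analysis for that objective (16.4.2.2).** The planned analysis reads: "The weekly CIPN20 scores will be summarized at each time point by mean (SD) and median (range) and will be plotted longitudinally". This is done by arm, with the two placebo groups pooled. No difference between arms is specified.
- **Contingent models (16.5, called as sensitivity analysis in 16.3.1).** If at least 10% of primary-endpoint assessments are missing, the mechanism is examined. A MAR finding leads to a linear mixed model with a patient random effect, treatment and the factors linked to missingness. An MNAR finding leads to exploratory pattern-mixture or selection models. An MCAR finding leads to complete-case analysis.
- **Sample size (16.2.1).** The size rests on feasibility and on estimating the difference "with a 95% two-sided confidence interval width of 16.8 points".

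**The concern.** The product of this pilot is an estimate with an interval, to be carried into a phase III design. Eight post-baseline scores per patient are collected, but in the routine plan weeks 1-7 enter a between-arm estimate only as the last score of an early discontinuer.

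The shape of the effect over time matters for phase III, because it bears on the choice of assessment time. The protocol treats it as open. Section 1.7.4 describes one meta-analysis in which the advantage of PEA grew over time and another with no association between efficacy and treatment duration, and it leaves the discrepancy to future studies. Separate curves for each arm show a pattern but attach no uncertainty to the difference between PEA and placebo.

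Section 16.5 does not fill the gap. Its models depend on the amount and judged mechanism of missingness, so the better the questionnaires are completed, the less likely any longitudinal model is run. The MAR model as described also names no week term and no arm-by-week term, so it is not set up to estimate a trajectory difference.

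**Working it through.** **Inputs from Section 16.2.1.** SD of the change score 15 in each arm; 26 per PEA arm against 26 pooled placebo; 95% two-sided. The documents give no between-week or baseline-to-week correlation, so every correlation below is an assumption. The weeks 5-8 window is also chosen here for illustration.

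**Step 1. The plan's own figure.** Width = 2 × t(0.975, 50 df) × 15 × √(1/26 + 1/26) = 16.71. The half-width is 8.36; rounded to 8.4 and doubled, it gives the stated 16.8. The figure reproduces.

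**Step 2. Interval for a weeks 5-8 average minus baseline.** Let Y0 to Y8 be the scores, with equal variance (set to 1). The width becomes 16.71 × f, where f² = Var(mean(Y5..Y8) − Y0) / Var(Y8 − Y0).

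- *Equal correlation ρ among all nine scores.* Numerator (1 + 3ρ)/4 + 1 − 2ρ = 1.25(1 − ρ); denominator 2(1 − ρ). So f² = 0.625 and f = 0.791 for any ρ.
- *AR(1), adjacent-week correlation 0.80.* Denominator 2(1 − 0.80⁸) = 1.664; numerator 0.774 + 1 − 2(0.242) = 1.290. So f² = 0.775 and f = 0.880.
- *Stable response: post-baseline weeks correlate at 0.9 with each other and at b with baseline.* Numerator (1 + 3 × 0.9)/4 + 1 − 2b = 1.925 − 2b; denominator 2 − 2b. For b = 0.5, f² = 0.925 and f = 0.962. For b = 0.6, f² = 0.725/0.800 = 0.906 and f = 0.952.

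**Step 3. Set the gain against dilution.** If the effect builds linearly to week 8, the average of weeks 5-8 holds (5 + 6 + 7 + 8)/(4 × 8) = 6.5/8 = 0.8125 of the week-8 effect. Effect divided by standard error, relative to week 8, is then 0.8125/f.

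| Assumed structure | Width | Narrower by | Effect/SE v week 8, linear build-up |
|---|---|---|---|
| Equal correlation, any ρ | 13.2 | 21% | 1.03 |
| Mixed: patient share 0.3-0.6, 15% noise, rest AR(1) 0.85 | 14.3-14.0 | 15-16% | 0.95-0.97 |
| AR(1), 0.80-0.95 | 14.7-14.5 | 12-13% | 0.92-0.94 |
| Post-baseline 0.9, baseline 0.5-0.6 | 16.1-15.9 | 4-5% | 0.84-0.85 |

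If the effect is flat over weeks 5-8, there is no dilution. The narrowing then equals a sample larger by a factor 1/f², from 1.08 (1/0.925) to 1.60 (1/0.625).

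**Step 4. The week-8 difference itself.** With complete data and an unstructured covariance, a model with arm-by-week terms gives essentially the same week-8 contrast as week 8 alone, so weeks 1-7 add almost nothing. Putting baseline in the model does narrow it, by a factor √((1 + ρ)/2), where ρ is the baseline-to-week-8 correlation (13% at ρ = 0.5, 5% at ρ = 0.8). That comes from baseline adjustment, not from the weekly scores.

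**The case against.** The strongest reply is that description suits an exploratory objective in a pilot. Objective 2.3.2 asks only to explore a trajectory, and no conclusion of the trial is invalid without a model. The weekly means and SDs, with the arm sizes, would also let a reader form unadjusted weekly differences and intervals. That stands, and it is why this is an improvement and not a correction of an error. A reader could not, however, recover baseline-adjusted differences or an average over weeks from those summaries, because both need the within-patient correlation.

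A second reply is that longitudinal models are already planned in Section 16.5. They are, and it would be wrong to say that the plan never uses the weekly scores. They remain conditional, and the mixed model as written has no time terms.

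A third reply concerns precision. A reader might infer that the planned interval is wider than the collected data allow, and might put a single firm figure on the excess. The documents do not support that. The planned interval is for the week-8 difference, which weeks 1-7 barely sharpen. The narrower interval is for another quantity, and its size depends on correlations found nowhere in the documents. Under linear build-up, effect over standard error falls in every structure tried except equal correlation. This reply stands in full.

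Finally, the addition brings 18 intervals (2 doses × 8 weeks, plus 2 averages) at 26 per arm. They need a rule for how they are read.

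**Conclusion.** The gap holds in a limited form. In the routine plan, weeks 1-7 serve for by-arm summaries and plots, apart from last-score substitution and the contingent models of Section 16.5. Objective 2.3.2 therefore has no PEA-minus-placebo estimate with an interval over time. This does not depend on any assumed correlation.

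The precision gain is secondary and uncertain: about 4-21% for a weeks 5-8 average across the structures tried, assuming equal variances over weeks, complete data and SD 15. It would be wrong to conclude that the primary analysis is inefficient or should be replaced. If benefit is still growing at week 8, the average understates the week-8 effect and the narrower interval may be no more informative. Section 1.7.4 leaves the shape unsettled. The case for the change is that a low-cost model answers a question the protocol itself raises.

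**What to change.** Keep the week-8 change as the primary analysis. Add to Section 16.4.2.2 one prespecified supportive repeated-measures model on all weekly CIPN20 scores, with arm, week, arm-by-week and baseline, run whatever the level of missingness. For each PEA dose against combined placebo, report with 95% intervals:

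1. the difference at each week;
2. a late-treatment average over weeks fixed in advance, for example weeks 5-8.

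Name the covariance structure in the text. Label the results as exploratory estimation, not to be read as separate tests, and state that the average is a different estimand from the week-8 difference and may understate an effect that builds. The fitted correlations would also be useful for planning phase III.

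The cost is a few lines of SAP text and one extra model, with no new data, visits or patients. The text should be fixed before unblinding, so that the choice of weeks cannot follow the results.
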